- Comparison of metabolic profiles of urine and stool samples from baseline to the end of intervention between grandmothers, mothers and daughters between dietary fibre intervention and placebo.
- Comparison of blood glucose levels from baseline to the end of intervention between grandmothers, mothers and daughters between dietary fibre intervention and placebo.
- Comparison of blood insulin levels from baseline to the end of intervention between grandmothers, mothers and daughters between dietary fibre intervention and placebo.
- Comparison of gut hormone levels from baseline to the end of intervention between grandmothers, mothers and daughters between dietary fibre intervention and placebo.
- Comparison of blood lipid levels from baseline to the end of intervention between grandmothers, mothers and daughters between dietary fibre intervention and placebo.
- Correlation of 3 days food diary information with gut bacteria production of SCFA among the 2 or 3 generations.

- Correlation of 3 days food diary information with gut bacteria composition among the 2 or 3 generations.
- Correlation of 3 days food diary information with urine metabolic profiles among the 2 or 3 generations.

6. Study methodology:

- Randomised, placebo controlled, double-blinded, cross-over study
- 4 weeks intervention (dietary fibre/placebo) 4 weeks wash-out 4 weeks intervention (opposite arm of intervention)

7. Intervention products:

The fibre intervention product will contain in equal proportions inulin, pectin and oat beta-glucan.

The placebo product will contain cellulose.

The intervention products will be sourced from Nestlé.

The fibre intervention and placebo products will be powders stored in sachets that will look identical and identically-packaged and participants will be able to add them to and mix them with their meals. The amount of intervention taken daily will be increased gradually (see below) to allow participants to adapt to the increased intake of dietary fibre and reduce the likelihood of gastrointestinal discomfort.

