Participants will be asked not to consume any intervention products on the study visit. At the end of study visits 1 and 3, participants will receive 56 sachets of intervention products. At study visits 2 and 4, participants will be asked to bring the empty sachets to assess compliance with the intervention. Throughout the 2 study intervention periods, participants will be asked to complete daily the Intervention Product Reminder sheet whenever they take the intervention product. This will also allow for assessing compliance with the intervention.

Intervention products will be stored in sachets and boxes in the Commonwealth Building of Hammersmith campus, Imperial College London.

8. Participants:

10 duos or trios (20-30 participants) females

Inclusion criteria:

- Any of the following groups of people (in direct descent and from the same family):
 - Grandmother, mother and daughter

- Mother and daughter
- Grandmother and granddaughter
- Age 18-85 (inclusive)
- BMI: 18.5-30 kg/m² (inclusive)
- Considering themselves healthy

Exclusion criteria:

- Intake of antibiotics in the past 3 months and during the study
- Intake of probiotic supplements in the past month and during the study
- Regular intake of laxatives in the past month and during the study
- Subjects with the following conditions:
 - Inflammatory Bowel Disease (IBD)
 - Irritable Bowel Syndrome (IBS)
 - Coeliac Disease
 - Type 12 Diabetes
 - Any type of cancer
 - Autoimmune conditions
 - Conditions that affect the liver
 - Conditions that affect the pancreas
- Subjects who require medical intervention in the coming 3 months
- Smokers
- Shift workers
- Gluten intolerance
- Pregnant and lactating women
- Subjects living in care homes
- had weight changes >5% in the preceding 3 months
- Subjects who are unable to give informed consent by themselves
- Subjects who are currently participating in other clinical trials

Support of number of volunteers:

This is a pilot exploratory study in a new area of research and therefore statistical power calculation is not possible.

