There is a 4-week gap (28 days +/-4 days) between Study Visits 1 and 2, followed by a 4-week wash-out period (28 days +/-7 days) and then followed by Study Visits 3 and 4 (4-week gap 28 days +/-4 days between Study Visits 3 and 4) (Figure 1).

[figure not shown]

Figure 1. Diagram of study visits; V=study visit

Participants will come fasted at the Study Visits and they will not have consumed any intervention products in the morning. They will bring their stool and urine samples, the 3 days food diaries and the participants questionnaire. They will also undergo a physical examination (body weight, height and fat percentage) and have their blood pressure measured and recorded. Women of childbearing age will have a pregnancy test at the beginning of each study visit. If the pregnancy test result is positive, they will be withdrawn from the study. No more data and samples will be collected from them. All the data and samples that were collected up to their withdrawal will be used in data analysis.

At Study Visits 2 and 4 participants will be asked to complete a Visual Analogue Questionnaire where they will rate how the dietary intervention has affected various gastrointestinal symptoms, such as constipation, bloating, appetite.

At 09:30 an intravenous cannula will be inserted into one arm for blood sampling by an adequately trained doctor, nurse or member of research team under aseptic conditions. Just before 10:00 fasting blood samples will be taken through an intravenous peripheral cannula (-15min and -5min). Participants will then receive a standardised breakfast at 10:00.

Postprandial blood samples will be taken at 15, 30, 45, 60, 90, 120 180 and 240 minutes after having the standardised breakfast to measure gut hormones, lipids, glucose, and insulin and inflammatory marker levels. 10ml of blood samples will be

taken at each sampling point, and therefore 100ml (10 x 10ml) during each study visit will be taken (Figure 2).

[figure not shown]

Figure 2. Diagram of Study Visit protocol; VAS=Visual Analogue Scale

Appetite and wellbeing will be assessed at the following timepoints (Figure 2): -15, 0, 30, 60, 120,180 and 240 minutes using a visual analogue scale (VAS).

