The collected samples (stool, urine and blood) will be analysed for: gut microbiota composition (from stools) through 16S rRNA sequencing and qPCR (quantitative Polymerase Chain Reaction); metabolites produced by the gut microbiota (from stools and urine) thorough NMR (Nuclear Magnetic Resonance), GC-MS (gas chromatography coupled with mass spectrometry), LC-MS (liquid chromatography coupled with mass spectrometry), LC-MS (liquid chromatography coupled with mass spectrometry), blood glucose, insulin, gut hormones (PYY and GLP-1), inflammatory markers (C reactive protein) and lipid levels.

11. Statistical Analysis

Statistical tests, such as ANOVA (Analysis of Variance) and t-tests (paired and unpaired) will be used to compare different groups: study participants groups, dietary fibre groups and placebo groups. Correlation analysis (Pearson and/or Spearman) and linear models will be used to analyse the relationship between gut bacteria taxa, short-chain fatty acids levels, metabolites levels, food diary information and demographics. Statistical significance levels will be p<0.05.

Various platforms will be used to analyse the data. Gut microbiome composition will be analysed using 16S rRNA sequencing on Illumina MiSeq and statistical analyses will be performed in R. Species diversity and richness will be calculated and statistical tests include t-tests and Mann-Whitney U tests, statistical significance p<0.05. Species diversity and richness and their changes from baseline between grandmother, mother and offspring will be compared. Data from placebo and dietary fibre intervention will be compared.

Short-chain fatty acids (SCFA) production from stool samples will be measured using GC-MS (Gas Chromatography coupled with Mass Spectrometry). T-tests (paired and/or unpaired) and ANOVA tests will be used to determine whether there are significant differences in SCFA production between grandmothers, mothers and offspring from baseline to end of intervention. Data from placebo and dietary fibre intervention will be compared. Significance levels will be p<0.05.

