NMR analysis will be done on urine and stool samples to examine and compare metabolic profiles between grandmothers, mothers and offspring and their changes from baseline to end of intervention. Multivariate data analysis, such as Principal Component Analysis will be used to examine and compare if there are chemicals that differentiate the profiles of grandmothers, mothers and offspring at baseline and at the end of intervention. Analyses will be done using the following software R, Matlab, Simca and Prism GraphPad.

Food diaries will be coded using the Dietplan software which will offer insight into participants dietary habits such as their macronutrient intake. The data will be analysed using ANOVA, t-tests in R and Prism GraphPad to examine potential differences and similarities between participants.

The PhD student will be assisted by [name] in analysing the data. She will only have access to anonymised data.

12. Withdrawal Criteria and Adverse Events

Withdrawal Criteria

The safety of the study participants takes priority. Any significant adverse event (as assessed by the researchers) will halt the study and the ethics committee and sponsor will be informed as per standard protocol. All adverse events will be recorded and investigators will review each adverse event as it arises. In addition, participants will be free to withdraw at any time and are not required to give a reason.

If one or two participant(s) of the study group decide(s) to withdraw or need(s) to be withdrawn from the study, the other participant(s) from the group can still continue to participate.

The researcher can withdraw the participant on any of the following grounds:

• Participant's request

- Participant is lost to follow-up
- Participant no longer fulfils the eligibility criteria during the study duration (e.g. participant becomes pregnant etc.)
- Participant develops a condition or illness that interferes with participant's ability to take part in the study
- The investigator reserves the right to withdraw participants in the interest of participant's safety and welfare
- The participant loses capacity to consent.

All data and samples that have been collected up to the withdrawal point will be analysed and used in the study. After withdrawal from the study, no more samples and data will be collected from the participant.

Adverse Event (AE): Any untoward medical occurrence in a patient or clinical study subject.

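### No test named for the SCFA primary outcome both keeps women and families with partial data and respects the pairing

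*Combined protocol and SAP*

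**What the plan says.** Section numbers are those in the body of the protocol.

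- **Design (Section 6):** "Randomised, placebo controlled, double-blinded, cross-over study". Each woman should supply a change in SCFA under fibre and another under placebo: Visits 1 to 2 in one period, Visits 3 to 4 in the other.
- **Sample (Section 8):** "10 duos or trios (20-30 participants) females". Mother-daughter and grandmother-granddaughter duos are eligible alongside trios. No power calculation or dropout rate is given.
- **Withdrawn women:** Section 12 states "All data and samples that have been collected up to the withdrawal point will be analysed and used in the study". Section 9 says of women withdrawn for pregnancy: "All the data and samples that were collected up to their withdrawal will be used in data analysis".
- **Their relatives (Section 12):** "the other participant(s) from the group can still continue to participate".
- **SCFA analysis (Section 11):** "T-tests (paired and/or unpaired) and ANOVA tests will be used to determine whether there are significant differences in SCFA production". The section does not say which test serves which comparison, or whether the ANOVA is one-way, blocked or repeated-measures.

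Section 11 also lists Mann-Whitney tests for diversity, and correlations and linear models for associations between variables. Its general list of tests is given as examples. The documents contain no analysis set, no missing-data rule, no rule for incomplete families, and no random effect for woman or family.

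**The concern.** The primary outcome compares SCFA change between products and between generations, so the data are paired twice: within woman and within family. Each named test handles partial data in one of two ways.

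- **Paired tests lose people.** A woman who leaves after Visit 2 or 3 has no fibre-placebo difference and drops out of that comparison. She keeps only her period-1 change. A woman whose relative is missing drops out of the paired comparison between those two generations. A three-generation ANOVA requiring complete blocks would exclude every duo, even with no withdrawals.
- **Unpaired tests and one-way ANOVA keep people but ignore the correlation.** Applied to fibre against placebo, they ignore that the same woman gave both values. Applied to generations, they ignore that the women are related.

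With 10 families, either route costs something. The and/or wording also leaves the choice open until the gaps in the data are known. Finally, complete-pair results assume that loss is unrelated to response. That can be doubted here, because Section 7 increases the product gradually to limit gut discomfort, and tolerance could plausibly go with fermentation and hence with SCFA.

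**Working it through.** The plan states no power or precision figure, so there is none to reproduce. From the documents: 10 families, 2 or 3 women each (10 × 2 = 20 to 10 × 3 = 30), two periods.

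Assumptions, none from the documents:
- a share w = 0.10 to 0.20 of women is lost at random;
- correlation between relatives f = 0 to 0.4 in the quantity compared;
- correlation between a woman's two period changes r = 0.3 to 0.7;
- unit SD.

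**1. Families left intact.** Expected share (1 − w)² for duos and (1 − w)³ for trios.
- Duos: 0.81 to 0.64, or 8.1 to 6.4 of 10.
- Trios: 0.729 to 0.512, or 7.3 to 5.1 of 10.

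**2. Two-generation contrast, 10 trios.**
- Complete pairs: variance 2(1 − f)/[10(1 − w)²].
- All available women: generalised least squares. Over every pattern of presence and absence, sum 10 × P(pattern) × the inverse correlation matrix of the women present; invert; take the variance of the difference of two generation means.
- Unpaired test: the variance it assumes is 2/[10(1 − w)].

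| w | f | Complete pairs | All women | Ratio | Square root of ratio | Unpaired, assumed | Ratio to all women |
|---|---|---|---|---|---|---|---|
| 0.10 | 0 | 0.2469 | 0.2222 | 1.11 | 1.05 | 0.2222 | 1.00 |
| 0.10 | 0.4 | 0.1481 | 0.1374 | 1.08 | 1.04 | 0.2222 | 1.62 |
| 0.20 | 0 | 0.3125 | 0.2500 | 1.25 | 1.12 | 0.2500 | 1.00 |
| 0.20 | 0.4 | 0.1875 | 0.1599 | 1.17 | 1.08 | 0.2500 | 1.56 |

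Complete pairs therefore have 1.08-1.25 times the variance, and intervals about 4-12% wider from the standard error alone.

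At f = 0.4 the 1.62 and 1.56 describe the variance that the unpaired test assumes. The true variance of the unpaired difference is 2/[10(1 − w)] − 2f/10. This is 0.2222 − 0.08 = 0.1422 and 0.2500 − 0.08 = 0.1700, or 1.04 and 1.06 times that of the model. The harm is mainly miscalibration.

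**3. Fibre-placebo contrast.** Let c women have both periods and m have one, split evenly between products.
- Complete pairs: 2(1 − r)/c.
- All women: 2/[c/(1 − r) + m/2].

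Example, c = 24, m = 6, r = 0.5: 1/24 = 0.0417 against 2/(48 + 3) = 0.0392, which is 5.9% lower. For r = 0.3, 0.5, 0.7 the reduction is 3.7%, 2.7%, 1.6% at 10% loss and 8.0%, 5.9%, 3.6% at 20% loss.

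**4. Unpaired test on paired fibre and placebo values.** It uses variance 2/n where the truth is 2(1 − r)/n. The standard error is overstated by 1/√(1 − r) = 1.20, 1.41, 1.83 at r = 0.3, 0.5, 0.7. By a normal approximation, a nominal 5% test then has a true level of about 1.9%, 0.6% and 0.03%. With n = 30, an assumed difference of 0.5 SD and r = 0.5, power is about 75% paired with all women, 65% paired with 24 kept, and 46% unpaired with all 30.

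**The case against.** A reader might infer that Section 11 contradicts Sections 9 and 12. The documents do not support that. They promise that data collected before withdrawal will be used, not that every value enters the primary contrast. Partial data can enter period-1 change, unpaired, correlation or descriptive analyses.

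Nor does the plan offer only paired and unpaired t-tests: ANOVA is named for SCFA, and the general list is open. This does not close the gap. One-way ANOVA ignores the pairing, standard repeated-measures ANOVA needs complete cases, and the linear models are assigned to associations.

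It would also be wrong to say that paired tests discard every woman or family with a gap. A woman leaving after Visit 2 keeps a paired baseline-to-end change for period 1, and a trio that loses one member still yields one between-generation pair.

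One could compare the model with complete trios and obtain larger ratios, but the plan names no complete-trio analysis. The relevant comparator for a two-generation paired test is the complete pair.

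Two further points stand. The largest complete-pair ratio, 1.25, occurs at family correlation 0, where an unpaired generation test loses nothing. An unpaired generation test on each woman's own fibre-minus-placebo difference also keeps the within-woman pairing and the relatives of withdrawn women, ignoring only family correlation. But it still omits women with one period.

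Finally, this is a self-described pilot: "This is a pilot exploratory study in a new area of research and therefore statistical power calculation is not possible". That explains the missing power calculation. It does not explain leaving the primary comparison open while setting a significance threshold.

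**Conclusion.** The concern holds as a weakness in the chosen methods. For the SCFA contrast, none of the named tests keeps the partial data that Sections 9 and 12 intend to use and also respects the pairing that the cross-over and family design create.

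The precision lost by restricting to complete pairs is modest: about 4-12% in interval width for a two-generation contrast, and about 2-8% of variance for fibre against placebo. The larger cost comes from an unpaired fibre-placebo test, which Section 11 permits. The exclusion of duos applies only if a complete-block three-generation ANOVA is what is meant, and the plan does not say.

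All sizes rest on assumed dropout and correlations, and on loss at random. The bias from symptom-related loss is not quantified. The change should be made, but the study does not fail without it.

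**What to change.** State in Section 11 that the main SCFA analysis is a likelihood-based mixed model of period change:

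- one row per woman per completed period;
- fixed effects for product, period, generation and product by generation;
- random effects for woman and family;
- small-sample degrees of freedom.

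Every woman with at least one completed period then enters, whether or not her relatives remain, and duos and trios are analysed together. Keep the complete-pair test as a sensitivity analysis. Report how many women have one and two periods, by generation and product. Women who leave before Visit 2 have no change value, so report them descriptively. A Visit 3 baseline without Visit 4 likewise stays outside the model.

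The cost is wording and modest programming, with no new data. The downside is reliance on a model and a missing-at-random assumption with only 10 families. Gut symptoms are not in the model, so symptom-related loss is only partly addressed. A family random intercept captures a shared level of change but not a shared response to product; state this limit. If the family variance cannot be estimated, report that and show the complete-pair result alongside.

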Serious Adverse Event (SAE): Any untoward and unexpected medical occurrence that:

- results in death
- is life- threatening refers to an event in which the subject was at risk of death at the time of the event; it does not refer to an event which hypothetically might have caused death if it was more severe.
- requires hospitalisation, or prolongation of existing inpatients' hospitalisation.
- results in persistent or significant disability or incapacity
- is a congenital abnormality or birth defect

Medical judgement should be exercised in deciding whether an AE is serious in other situations. Important AEs that are not immediately life threatening or do not result in death or hospitalisation but may jeopardise the subject or may require intervention to prevent one of the other outcomes listed in the definition above, should also be considered serious.

Reporting Procedures

All adverse event should be reported. Depending on the nature of the event the reporting procedures below should be followed. Any questions concerning adverse event reporting should be directed to the Chief Investigator in the first instance.

Non-serious AEs

All such events, whether expected or not, should be recorded.

Serious AEs (SEAs)

An SAE form should be completed and faxed to the Chief Investigator within 24 h. However, relapse, death and hospitalisations for elective treatment of a pre-existing condition do not need reporting as SAEs.

All SAEs should be reported TBC Research Ethics Committee where in the opinion of the Chief Investigator the event was:

- 'related', i.e. resulted from the administration of any of the research procedures; and
- 'unexpected', i.e. an event that is not listed in the protocol as an expected occurrence.

Reports of related and unexpected SAEs should be submitted within 15 days of the Chief Investigator becoming aware of the event, using the NRES SAE form for non-IMP studies. The Chief Investigator must also notify the Sponsor of all SAEs.

Local investigators should report any SAEs as required by their Local Research Ethics Committee, Sponsor and/or Research & Development Office.

Contact details for reporting SAE:

Contact details for reporting SAEs [contact] CI email (and contact details below) Fax: xxx, attention xxx Please send SAE forms to: xxx

[name] through his secretary Mon to Fri 9 am-5 pm: [name]. Incidental Findings

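### Section 12 makes death a criterion for a serious adverse event and then exempts death from serious adverse event reporting

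*Combined protocol and SAP*

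**What the plan says.** All the reporting text is in Section 12, Withdrawal Criteria and Adverse Events.

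- **Definition.** The lead-in reads "Serious Adverse Event (SAE): Any untoward and unexpected medical occurrence that", and the first listed criterion is "results in death".
- **Form.** Under Reporting Procedures: "An SAE form should be completed and faxed to the Chief Investigator within 24 h".
- **Exemption.** The next sentence reads: "However, relapse, death and hospitalisations for elective treatment of a pre-existing condition do not need reporting as SAEs".
- **Ethics committee.** SAEs that the Chief Investigator considers both related and unexpected go to the committee: "Reports of related and unexpected SAEs should be submitted within 15 days of the Chief Investigator becoming aware of the event". Unexpected is explained as "an event that is not listed in the protocol as an expected occurrence".
- **Sponsor.** "The Chief Investigator must also notify the Sponsor of all SAEs".
- **General clause, under Withdrawal Criteria.** "Any significant adverse event (as assessed by the researchers) will halt the study and the ethics committee and sponsor will be informed", following a standard procedure that the document does not set out.

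Section 7 adds that emergency unblinding may be triggered by the need for expedited committee reporting of an unexpected and related SAE.

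**The concern.** The same section treats death as the leading example of an SAE and also says it need not be reported as one. Staff who follow the exemption to the letter could leave a participant's death out of SAE reporting without deviating from the protocol. The form, the sponsor notice and the committee report all depend on SAE handling, so one sentence could affect all three. The unblinding trigger in Section 7 could be affected in the same way.

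The exemption has no evident rationale here. Exempting relapse or death might make sense where they are endpoints of the disease under study. Section 8 instead enrols women who consider themselves healthy and excludes, among other conditions, cancer, inflammatory bowel disease and autoimmune, liver and pancreatic conditions. Relapse is not defined, and the trial studies no disease that could relapse.

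What is at stake is safety oversight in a trial that accepts participants up to age 85.

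**Working it through.** **Step 1: the scope of the exemption.** The sentence lists three items: relapse, death, and hospitalisations for elective treatment of a pre-existing condition. The closing qualifier fits only the third, because a death for elective treatment has no meaning. Nothing limits the exemption to unrelated or expected deaths, and no other section does so.

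**Step 2: what depends on SAE handling.**

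| Step in Section 12 | Trigger | Stated time limit | Could a death miss it under the exemption? |
|---|---|---|---|
| Form to Chief Investigator | SAE | 24 h | Yes |
| Notice to sponsor | All SAEs | None | Yes, on the general reading |
| Report to ethics committee | Related and unexpected SAE | 15 days | Yes, on the general reading, for such deaths |
| Local investigators' reports | SAE, as local bodies require | None | Yes, on the general reading |
| Study halt, committee and sponsor informed | Significant event, as judged by researchers | None | Not exempted, but depends on judgement |
| General duty to report all adverse events | Any adverse event | None | Not exempted, but refers to the procedures that contain the exemption |

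The first three rows are the protocol's own SAE-triggered steps.

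**Step 3: exposure.** Section 9 gives 28 ± 4 days, 28 ± 7 days and 28 ± 4 days between successive study visits. Section 8 gives 20-30 participants.

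- Nominal duration: 28 + 28 + 28 = 84 days
- Shortest: 24 + 21 + 24 = 69 days
- Longest: 32 + 35 + 32 = 99 days

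Person-years = participants × days / 365.25:

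- 20 × 69 / 365.25 = 3.8
- 20 × 84 / 365.25 = 4.6
- 30 × 84 / 365.25 = 6.9
- 30 × 99 / 365.25 = 8.1

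**Step 4: how likely a death is.** The documents give no mortality rate, so 0.1% to 3% per year is an assumption. Expected deaths = person-years × rate:

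- Low end: 3.78 × 0.001 = 0.004
- High end: 8.13 × 0.03 = 0.24

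The high end applies the top rate to every participant. With 10 families, at most 10 women are the oldest in their family. Taking 3% for those 10 and 0.1% for the other 20 over 99 days gives (10 × 0.03 + 20 × 0.001) × 99 / 365.25 = 0.087.

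**Step 5: the word unexpected.** It is part of the SAE definition and is then applied again as a separate test for committee reporting (Section 12) and for reporting-related unblinding (Section 7). A second test makes sense only if some SAEs are expected, which the definition rules out. The practical effect is small because the protocol lists no expected events.

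**The case against.** The conflict in wording is hard to dispute, but its consequences can be argued down in four ways.

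- **Narrow reading.** The exemption directly follows the sentence on the 24-hour form and does not amend the definition. A death would then still be an SAE for the sponsor notice and the committee report, and only the form would be lost. This reading is possible. But the exemption is worded generally, about reporting as SAEs, and the later duties concern SAEs. The text does not settle the matter, so the three-step loss is what could happen, not what must.
- **Life-threatening criterion.** A fatal event will often also qualify as life-threatening or involve hospitalisation, and could be reported on that ground. This largely stands. It narrows the gap, which is clearest for a sudden death outside hospital. Even there, one could argue that the participant was at risk of death at the time of the event. But a reader should not have to rely on that argument to report a death.
- **Significant-event clause.** Once triggered it is mandatory, and researchers would very probably judge a death significant. It also refers to a standard procedure that may carry its own deadline. This stands as a partial safeguard. Within the document, however, the trigger is a judgement, with no stated deadline and no required form.
- **Rarity.** Expected deaths are few, and the upper figure of 0.24 is generous. This is accepted; the conclusion does not rest on frequency.

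**Conclusion.** The concern holds and should be fixed before the protocol is relied on. Section 12 contradicts itself on whether a death is reported as an SAE, and nothing else in the document resolves it. On the general reading, three SAE-triggered steps could be missed, the third only for a related and unexpected death. On the narrow reading, one could be missed, the 24-hour form. Either is a defect for the most serious outcome the protocol names.

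The exposure and mortality figures show only that the event is improbable. They assume a reporting period from Visit 1 to Visit 4, which the document does not state (consent is taken at Visit 0), and an assumed mortality range. The severity rests on the written rule. The double use of unexpected is a minor drafting point and adds nothing to that severity.

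**What to change.** Amend Section 12 so that death is not both an SAE criterion and exempt from SAE reporting. The simplest edit is to remove relapse and death from the exemption sentence, leaving only hospitalisations for elective treatment of a pre-existing condition.

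As a secondary clarification, remove the requirement of unexpectedness from the SAE definition and keep it only as the test for expedited committee reporting, which agrees with the unblinding text in Section 7.

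The cost is a short protocol amendment and at most a few more SAE forms. Sample size, visits and analysis are unaffected.
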